### 10.4.4 Multiplicity Considerations

[REDACTED]  
[REDACTED]  
[REDACTED]  
[REDACTED].

#### 10.4.6 Secondary Efficacy Analyses

For secondary efficacy endpoints during the [REDACTED] CAE, [REDACTED]

[REDACTED]

[REDACTED]

[REDACTED]

The primary efficacy analysis [REDACTED]

[REDACTED] will be analyzed [REDACTED]

[REDACTED]

Primary analyses of secondary efficacy endpoints will utilize the ITT population with observed data only.

#### 10.4.7 Exploratory Efficacy Analyses

For efficacy endpoints recorded [REDACTED]

[REDACTED]

[REDACTED]

[REDACTED] will be utilized.

[REDACTED]

[REDACTED]

[REDACTED]

[REDACTED]

[REDACTED]

All efficacy analyses conducted on the ITT population will be conducted using the Initial Cohort population only with observed data.

Additional exploratory efficacy analyses may be conducted. Further details of the exploratory analysis plan will be described in SAP.

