## 10.4 Statistical Analysis

### 10.4.1 General Considerations

Quantitative variables will be summarized descriptively using number of subjects (n), mean, standard deviation, median, minimum, and maximum. Qualitative variables will be summarized using counts and percentages.

All summaries will be presented by treatment group. Summaries will be provided for demographics, baseline medical history, concurrent therapies, and subject disposition.

For the purpose of summarization, medical history, concurrent therapies, and adverse events will be coded to MedDRA and WHODrug dictionaries, as appropriate.

Baseline measures are defined [REDACTED]

[REDACTED] [REDACTED]  
[REDACTED] [REDACTED]  
[REDACTED]

All analyses will be [REDACTED] will be provided where appropriate.

The statistical analysis plan (SAP) will detail the statistical procedures, and will dominate any text herein.

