ANCOVA	Analysis of Covariance
ATC	Anatomical Therapeutic Chemical
CAC	Conjunctival Allergen Challenge
CAE®	Controlled Adverse Environment®
CI	Confidence Interval
CS	Clinically Significant
DED	Dry Eye Disease
eCRF	Electronic Case Report Form
EDC	Electronic Data Capture
ETDRS	Early Treatment of Diabetic Retinopathy Study
ICH	International Conference on Harmonisation
IOP	Intraocular Pressure
ITT	Intent-to-Treat
IWRS	Interactive Web Response System
logMAR	Logarithm of the Minimum Angle of Resolution
LS	Least Squares
MAR	Missing at Random
MCMC	Markov Chain Monte Carlo
MedDRA	Medical Dictionary for Regulatory Activities
MMRM	Mixed Model Repeated Measures
MNAR	Missing Not at Random
NCS	Not Clinically Significant
OD	Oculus dexter (Right Eye)
OS	Oculus sinister (Left Eye)
PDF	Portable Document Format
PMM	Pattern Mixture Model
PP	Per Protocol
PT	Preferred Term
RASP	Reactive Aldehyde Species
RDC	Remote Data Capture
RTF	Rich Text Format
SAE	Serious Adverse Event
SAP	Statistical Analysis Plan
SD	Standard Deviation
SDC	Statistics & Data Corporation
SDTM	Study Data Tabulation Model
SE	Standard Error
SOC	System Organ Class
TEAE	Treatment-Emergent Adverse Event
TMF	Trial Master File
VAS	Visual Analog Scale

WHODrug

World Health Organization Drug Dictionary

1. Introduction

The purpose of this statistical analysis plan (SAP) is to describe the planned analyses and reporting for protocol ADX-102-DED-019, Amendment 3.0, dated 5-NOV-2021.

This SAP is being written with due consideration of the recommendations outlined in the most recent International Conference on Harmonisation (ICH) E9 Guideline entitled Guidance for Industry: Statistical Principles for Clinical Trials, E9(R1) Statistical Principles for Clinical Trials: Addendum: Estimands and Sensitivity Analysis in Clinical Trials, and the most recent ICH E3 Guideline entitled Guidance for Industry: Structure and Content of Clinical Study Reports.

This SAP describes the data that will be analyzed and the subject characteristics, efficacy, and safety assessments that will be evaluated. This SAP provides details of the specific statistical methods that will be used. The statistical analysis methods presented in this document will supersede the statistical analysis methods described in the clinical protocol. If additional analyses are required to supplement the planned analyses described in this SAP, they may be completed and will be identified in the clinical study report.

2. Study Objectives

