8.1 Intent-to-Treat

The Intent-to-Treat (ITT) Population includes all randomized subjects. Subjects in the ITT Population will be analyzed as randomized. Subjects in the initial cohort will not be included in the ITT Population for efficacy analyses.

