8.4 Safety

The Safety Population includes all randomized subjects who receive at least one dose of investigational product. Subjects in the Safety Population will be analyzed as treated. The Safety Population includes subjects in the initial cohort who receive at least one dose of investigational product.

9. General Statistical Considerations

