14.3.9 OCULAR DISCOMFORT SCALE (ORA CALIBRA® SCALE) [REDACTED] [REDACTED]

For ocular discomfort [REDACTED]

15. Efficacy Analyses of the Initial Cohort

All efficacy analyses stated in section 14 using the ITT population will be repeated using the Initial Cohort only with the following exceptions:

16. Summary of Efficacy Analyses

A summary of all efficacy analyses will be presented.

17. Safety Analyses

All safety analyses will be conducted using the Safety Population using observed data only.

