17.5 Intraocular Pressure (IOP)

Subjects' IOP [REDACTED]

[REDACTED]

[REDACTED]

[REDACTED] . A subject listing of IOP will also be produced.

18. Changes from Protocol-Stated Analyses

There are no changes from protocol-stated analyses.

19. References

No references cited.

20. Revision History

Documentation of revision to the SAP will commence after approval of the final version 1.0.

[figure not shown]
20.1 Revision 01

This revision was issued following [REDACTED]

[REDACTED]

[REDACTED]

[REDACTED]

21. Tables

Tables (10 tables) in **boldface** font will be delivered in topline package.

Table Number	Title	Population
Table 14.1.1	Subject Disposition	All Screened Subjects
Table 14.1.2.1	Demographics	ITT Population
Table 14.1.2.2	Demographics	Safety Population
Table 14.1.2.3	Participation in Previous Reproxalap Trials	ITT Population
Table 14.1.3.1	Baseline Disease Characteristics	ITT Population
Table 14.1.3.2	Baseline Disease Characteristics	Safety Population
Table 14.1.4.1	Ocular Medical History	ITT Population

Table 14.1.4.2	Non-Ocular Medical History	ITT Population
Table 14.1.5.1	Ocular Concomitant Medications	ITT Population
Table 14.1.5.2	Non-Ocular Concomitant Medications	ITT Population
Table 14.1.5.3	Ocular Concomitant Procedures	ITT Population
Table 14.1.5.4	Non-Ocular Concomitant Procedures	ITT Population
Table 14.2.1.1	Overall Mean Change from Baseline of Conjunctival Redness (Ora Calibra Scale) during [REDACTED]	ITT Population with Observed Data Only
Table 14.2.1.2	Overall Mean Change from Baseline of Conjunctival Redness (Ora Calibra Scale) [REDACTED]	PP Population with Observed Data Only
Table 14.2.1.3	Overall Mean Change from Baseline of Conjunctival Conjunctival Redness (Ora Calibra Scale) [REDACTED] [REDACTED]	ITT Population with Observed Data Only
Table 14.2.1.4	Overall Mean Change from Baseline of Conjunctival Conjunctival Redness (Ora Calibra Scale) [REDACTED] [REDACTED]	ITT Population with Observed Data Only
Table 14.2.1.5	Overall Mean Change from Baseline of Conjunctival Redness (Ora Calibra Scale) [REDACTED]	ITT Population with PMM
Table 14.2.1.6	Overall Mean Change from Baseline of Conjunctival Redness (Ora Calibra Scale) [REDACTED]	ITT Population with MCMC
Table 14.2.2.1	Overall Mean Change from Baseline of Eye Dryness (Visual Analog Scale) [REDACTED] [REDACTED]	ITT Population with Observed Data Only

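### Are the ITT efficacy analyses confined to the 20-subject Initial Cohort, and does any baseline table describe the set that is tested?

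*Protocol*

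**What the plan says.** Protocol 10.4.7 and the synopsis carry the same sentence: "All efficacy analyses conducted on the ITT population will be conducted using the Initial Cohort population only with observed data". Protocol 10.4.5 and 10.4.6 put the primary and secondary analyses on the ITT population with observed data, and Protocol 10.3 plans for 149 evaluable subjects per arm.

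SAP 8.1 first defines the set broadly, "The Intent-to-Treat (ITT) Population includes all randomized subjects", and then restricts it: "Subjects in the initial cohort will not be included in the ITT Population for efficacy analyses". SAP 15 says that the Section 14 analyses on ITT "will be repeated using the Initial Cohort only with the following exceptions". SAP 8.4 keeps the Initial Cohort in the other main set: "The Safety Population includes subjects in the initial cohort who receive at least one dose of investigational product".

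On precedence, Protocol 10.4.1 says that the SAP "will dominate any text herein", and SAP 1 says that its methods "will supersede the statistical analysis methods described in the clinical protocol". SAP 18 nevertheless records: "There are no changes from protocol-stated analyses".

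**The concern.** Two things look wrong.

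First, on its face the protocol sentence moves all ITT efficacy testing into a cohort of about 20 subjects. SAP 8.1 excludes exactly those subjects, and SAP 18 declares no departure from the protocol. If the sentence were followed, the trial would have almost no power. If the two cohorts were instead pooled, subjects already unmasked for the sample-size work (SAP 5.2) would enter the confirmatory test.

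Second, SAP 8.1 attaches its exclusion to efficacy analyses. Demographics, baseline characteristics, medical history and concomitant treatment are not efficacy analyses, so the ITT tables for them could hold about 320 subjects while the ITT efficacy tables hold about 300. The Safety versions also include the Initial Cohort. A reader checking whether the arms were comparable at baseline in the tested set would then have no table for exactly that set. The 20 subjects also differ by design: they come from one site and were randomised from a paper list rather than by IWRS.

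**Working it through.** **1. Which set is tested?** The 149 per arm cannot be reproduced, because the difference, SD, power and alpha are redacted. It can be compared with the cohort sizes:

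- Main Cohort: about 300, or 150 per arm. 2 × 149 = 298, and 298/300 = 99.3%.
- Initial Cohort: 20, or 10 per arm.

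To see what the literal reading implies, assume two-sided alpha of 0.05 or 0.025 and planned power of 80% to 95%. The standardised effect implied by 149 per arm is d = (z for alpha/2 + z for power) × √(2/149).

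| Alpha (assumed) | d at 80% to 95% power | Power at 10 per arm |
|---|---|---|
| 0.05 | 0.325 to 0.418 | 10.9% to 15.2% |
| 0.025 | 0.357 to 0.450 | 7.5% to 10.8% |

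The sample size was therefore not set for a 20-subject test.

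**2. How the sentence reads beside its neighbours.** The word *only* can attach to the cohort or to the observed data. Protocol 10.4.5 and 10.4.6 attach it to observed data. In SAP 21, the 13 Initial Cohort efficacy tables (14.2.4.1 to 14.2.4.13) carry the same observed-data qualifier and stand apart from the ITT efficacy tables. SAP 15 describes a repeat, not a replacement. Every other visible statement fits one reading: test in the Main Cohort, and repeat in the Initial Cohort with observed data.

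**3. Table counts from SAP 21.**

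- ITT, not efficacy: 14.1.2.1, 14.1.2.3, 14.1.3.1, 14.1.4.1, 14.1.4.2 and 14.1.5.1 to 14.1.5.4, which makes 9.
- ITT, efficacy: 5 (14.2.1.1 and 14.2.1.3 to 14.2.1.6) + 5 (14.2.2.x) + 11 (14.2.3.x) = 21.
- Per-protocol: 1 (14.2.1.2), an efficacy table. The SAP 8.1 exclusion reaches it through ITT, so the per-protocol definition in SAP 8.3 raises no separate issue.

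**4. Size, if the nine tables do include the Initial Cohort.** The share is 20/(20 + 300) = 6.25%. The shift in a tabulated mean is 0.0625 × the difference between the cohort means. For assumed differences of 0.25, 0.5 and 1.0 SD this gives 0.016, 0.031 and 0.063 SD.

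For the difference between arms, the shift is (10/160) × (Initial Cohort difference − Main Cohort difference). Under randomisation its SD is 0.0625 × √(2/10 + 2/150) = 0.029, so 95% of shifts lie within 1.96 × 0.029 = 0.057 SD.

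**The case for a change.** The strongest case for acting is that both documents are literally wrong somewhere. The protocol sentence is complete, unredacted and stated twice. The synopsis also promises that the SAP will detail any change to protocol-stated analyses, yet SAP 18 reports none. In SAP 8.1 the efficacy qualifier must limit something: an exclusion from every ITT output would not need it. ITT and Safety are defined differently (as randomised against as treated), which alone could explain paired tables, so the pairing does not prove that the ITT versions are Main Cohort only. The remedy would be a few words and a population flag.

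Part of this stands. The protocol sentence is badly worded, and on its literal reading SAP 18 is inaccurate. On the text of SAP 8.1 alone, including the Initial Cohort in the nine tables is a fair reading.

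The step from there to a defect in the plan does not stand. Precedence is stated in both documents, so the wording cannot change which analysis is run. SAP 8.1 does not expressly say which set the ITT baseline tables use, and parts of SAP 11 and 12 that might say so are redacted, so it cannot be asserted that no table describes the tested set. Redefining ITT as the Main Cohort also has a price: the Initial Cohort's history and concomitant medications would then appear only in Listings 16.2.4.2 to 16.2.4.5.

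**Conclusion.** No change is called for. The protocol sentence is a clerical slip, in effect a missing comma or *also*. An analyst following the SAP will test efficacy in the Main Cohort and repeat the analyses in the Initial Cohort, which is also what the table list and the 149 per arm imply.

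The baseline denominator is a small gap that the programming team can fill by stating the N on each table. At most it concerns 20 of about 320 subjects. It moves a descriptive mean by 0.016 to 0.063 SD and a between-arm baseline difference by no more than about 0.06 SD in 95% of cases. The primary model takes the baseline score as a covariate in the tested subjects (Protocol 10.4.5), so no test draws on these tables. Population membership and demographics are also listed by subject (Listings 16.2.3.1 and 16.2.4.1).

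The sizes rest on cohorts of 20 and about 300, 1:1 allocation, the assumed 0.25 to 1.0 SD difference between cohorts, and a common SD. The power figures rest on assumed alpha and power, since the documents' own values are redacted; they serve only to show that a 20-subject test was never intended.

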#### 10.4.8 Safety Variables

Adverse events will be coded using the MedDRA dictionary.

Frequencies and percentages will be provided per treatment group of subjects with treatment-emergent adverse events (TEAEs), serious TEAEs, and TEAEs causing premature discontinuation. An adverse event is treatment-emergent if it occurs or worsens after the first dose of randomized study treatment. Furthermore, frequencies will be given of subjects with TEAEs by system organ class, by system organ class and preferred term, by system organ class, preferred

term and maximal severity, by system organ class, preferred term and strongest relationship, and by system organ class, preferred term, maximal severity, and strongest relationship. Separate analyses will be performed for ocular specific and all adverse events (including systemic).

## 11 COMPLIANCE WITH GOOD CLINICAL PRACTICES, ETHICAL CONSIDERATIONS, AND ADMINISTRATIVE ISSUES

The ADX-102-DED-019 clinical trial will be conducted in compliance with the protocol, current Good Clinical Practices (GCPs), including the International Council for Harmonization (ICH) Guidelines, and in general, consistent with the Declaration of Helsinki. In addition, all applicable local, state, and federal requirements in the countries involved will be adhered to.

### 11.1 Protection of Human Subjects

#### 11.1.1 Subject Informed Consent

Informed consent/assent must take place before any study specific procedures are initiated. Signed and dated written informed consent must be obtained from each subject and/or from the legal guardian prior to enrollment into the study.

All informed consent/assent forms must be approved for use by Ora and receive approval/favorable opinion from an IRB prior to their use. If the consent form requires revision (e.g., due to a protocol amendment or significant new safety information), it is the investigator's responsibility to ensure that the amended informed consent is reviewed and approved by sponsor prior to submission to the governing IRB and that it is read, signed and dated by all subjects subsequently enrolled in the study as well as those currently enrolled in the study. If informed consent is taken under special circumstances (oral informed consent), then the procedures to be followed must be determined by Ora and provided in writing by Ora prior to the consent process.

#### 11.1.2 Institutional Review Board (IRB) Approval

The ADX-102-DED-019 clinical trial is to be conducted in accordance with Institutional Review Board regulations (U.S. 21 CFR Part 56.103). The investigator must obtain appropriate IRB approval before initiating the trial and re-approval at least annually.

Only an IRB approved version of the informed consent form will be used.

## 11.2 Ethical Conduct of the Study

The ADX-102-DED-019 clinical trial will be conducted in accordance with the ethical principles that originated with the Declaration of Helsinki.

## 11.3 Subject Confidentiality

All personal study subject data collected and processed for the purposes of this trial should be maintained by the investigator and his/her staff with adequate precautions as to ensure that the confidentiality of the data in accordance with local, state, and federal laws and regulations.

Monitors, auditors and other authorized representatives of Ora, the IRB approving this trial, the FDA, the DHHS, other domestic government agencies, and other foreign regulatory agencies will be granted direct access to the study subject's original medical and study records for verification of the data and clinical trial procedures. Access to this information will be permitted to the aforementioned individuals to the extent permitted by law.

## 11.4 Documentation

Source documents may include a subject's medical records, hospital charts, clinic charts, the investigator's study subject files, as well as the results of diagnostic tests such as X-rays, laboratory tests, and EKGs. The investigator's copy of the source documents serves as the investigator's record of a subject's study-related data.

### 11.4.1 Retention of Documentation

All trial related correspondence, patient records, consent forms, and copies of source documents should be maintained on file for at least two years. These documents will be retained for a longer period if required by the applicable regulatory requirements or by an agreement with the Sponsor. It is the responsibility of the Sponsor to inform the investigator/institution as to when these documents no longer need to be retained.

If the responsible investigator retires, relocates, or for other reasons withdraws from the responsibility of keeping study records, custody must be transferred to a person who will accept the responsibility. Ora must be notified in writing of the name and address of the new custodian.

## 11.5 Labeling, Packaging, Storage, Accountability, and Return or Disposal of Study Drug

### 11.5.1 Labeling/Packaging

Investigational drug will be packaged and labeled into clinical kits.

Each pouch will contain five ampules to provide a sufficient supply of randomized study drug.

#### **11.5.2 Storage of Study Drug**

The study drug must be stored in a secure area accessible only to the investigator and his/her designees. The study drug will be administered only to subjects entered into the clinical study, in accordance with the conditions specified in this protocol. [REDACTED]

[REDACTED]

[REDACTED]

[REDACTED]

#### **11.5.3 Accountability of Study Drug**

The study drug is to only be prescribed by the principal investigator or his/her named sub investigator(s), and is to only be used in accordance with this protocol. The study drug must only be distributed to subjects properly qualified under this protocol to receive study drug. The investigator must keep an accurate accounting of the study drug by maintaining a detailed inventory. This includes the amount of study drug received by the site, amount dispensed to subjects, amount returned to the site by the subjects, and the amount returned to the Sponsor upon the completion of the study.

#### **11.5.4 Return or Disposal of Study Drug**

All study drug will be returned to the sponsor or their designee or destroyed on behalf of the Sponsor following local regulations.

### **11.6 Recording of Data on Source Documents and electronic Case Report Forms (eCRFs)**

The investigator is responsible for ensuring that study data is completely and accurately recorded on each subject's eCRF and all study-related material. All study data should also be attributable, legible, contemporaneous, and original. Recorded datum should only be corrected in a manner that does not obliterate, destroy, or render illegible the previous entry (e.g., by drawing a single line through the incorrect entry and writing the revision next to the corrected data). An individual who has corrected a data entry should make clear who made the correction and when, by adding to the correction his/her initials as well as the date of the correction.

### **11.7 Handling of Biological Specimens**

See Appendix 2 "Examination Procedures, Tests, Equipment, and Techniques" for tear collection procedures. Processing, shipping, and handling procedures will be done by following the Laboratory Manual.

## 11.8 Publications

Authorship and manuscript composition will reflect cooperation among all parties involved in the study. Authorship will be established before writing the manuscript. Ora will have the final decision regarding the manuscript and publication.

## **Appendix 1: Schedule of Visits and Measurements**

[figure not shown]
## Appendix 2: Examination Procedures, Tests, Equipment, and Techniques

[figure not shown]

[figure not shown]

[figure not shown]

[figure not shown]

**Appendix 3: Amendment Summary of Changes Table**

[figure not shown]

ANCOVA	Analysis of Covariance
ATC	Anatomical Therapeutic Chemical
CAC	Conjunctival Allergen Challenge
CAE®	Controlled Adverse Environment®
CI	Confidence Interval
CS	Clinically Significant
DED	Dry Eye Disease
eCRF	Electronic Case Report Form
EDC	Electronic Data Capture
ETDRS	Early Treatment of Diabetic Retinopathy Study
ICH	International Conference on Harmonisation
IOP	Intraocular Pressure
ITT	Intent-to-Treat
IWRS	Interactive Web Response System
logMAR	Logarithm of the Minimum Angle of Resolution
LS	Least Squares
MAR	Missing at Random
MCMC	Markov Chain Monte Carlo
MedDRA	Medical Dictionary for Regulatory Activities
MMRM	Mixed Model Repeated Measures
MNAR	Missing Not at Random
NCS	Not Clinically Significant
OD	Oculus dexter (Right Eye)
OS	Oculus sinister (Left Eye)
PDF	Portable Document Format
PMM	Pattern Mixture Model
PP	Per Protocol
PT	Preferred Term
RASP	Reactive Aldehyde Species
RDC	Remote Data Capture
RTF	Rich Text Format
SAE	Serious Adverse Event
SAP	Statistical Analysis Plan
SD	Standard Deviation
SDC	Statistics & Data Corporation
SDTM	Study Data Tabulation Model
SE	Standard Error
SOC	System Organ Class
TEAE	Treatment-Emergent Adverse Event
TMF	Trial Master File
VAS	Visual Analog Scale

WHODrug

World Health Organization Drug Dictionary

1. Introduction

The purpose of this statistical analysis plan (SAP) is to describe the planned analyses and reporting for protocol ADX-102-DED-019, Amendment 3.0, dated 5-NOV-2021.

This SAP is being written with due consideration of the recommendations outlined in the most recent International Conference on Harmonisation (ICH) E9 Guideline entitled Guidance for Industry: Statistical Principles for Clinical Trials, E9(R1) Statistical Principles for Clinical Trials: Addendum: Estimands and Sensitivity Analysis in Clinical Trials, and the most recent ICH E3 Guideline entitled Guidance for Industry: Structure and Content of Clinical Study Reports.

This SAP describes the data that will be analyzed and the subject characteristics, efficacy, and safety assessments that will be evaluated. This SAP provides details of the specific statistical methods that will be used. The statistical analysis methods presented in this document will supersede the statistical analysis methods described in the clinical protocol. If additional analyses are required to supplement the planned analyses described in this SAP, they may be completed and will be identified in the clinical study report.

2. Study Objectives

To evaluate the efficacy of reproxalap, as assessed by conjunctival redness, tear reactive aldehyde species (RASP) levels, Schirmer's Test, and symptoms after dosing [REDACTED] to the Controlled Adverse Environment® (CAE®) in subjects with dry eye disease (DED).

3. Study Endpoints

